Trial Title

An Open-Label, Multicenter, Phase I/II Clinical Trial to Evaluate the Safety, Tolerability, Efficacy, and PK/PD Characteristics of SR604 Injection in Patients with Hemophilia A/B and Congenital Coagulation Factor VII Deficiency

Investigational Medicinal Product

SR604 Injection

Protocol Number

LS-SR604-I01

Version Number/Date

Ver 3.1 / 13 January 2026

Sponsor

Shanghai RAAS Blood Products Co., Ltd.

Trial Sites

It is planned to select 6 sites as clinical trial institutions

Trial Phase

Phase I/II

Trial Population

Patients with Hemophilia A/B and congenital coagulation Factor VII deficiency

Trial Objectives

Part A:

Primary objective: To evaluate the safety, tolerability, and immunogenicity of SR604 following a single administration in patients with Hemophilia A/B;

Secondary objective: To evaluate the pharmacokinetic characteristics of SR604 following a single administration in patients with Hemophilia A/B;

Exploratory objective: To explore the pharmacodynamic characteristics of SR604 following a single administration in patients with Hemophilia A/B.

Part B / Part C:

Primary objective: To evaluate the efficacy of SR604 following multiple administrations in patients with Hemophilia A/B and congenital coagulation Factor VII deficiency.

Secondary objectives: To evaluate the pharmacokinetic characteristics of SR604 following multiple administrations in patients with Hemophilia A/B and congenital coagulation Factor VII deficiency; to evaluate the safety and additional efficacy endpoints of SR604 following multiple administrations in patients with Hemophilia A/B and congenital coagulation Factor VII deficiency.

Exploratory objective: To explore the pharmacodynamic characteristics of SR604 following multiple administrations in patients with Hemophilia A/B and congenital coagulation Factor VII deficiency.

Trial Endpoints

Part A:

Primary endpoints (safety and immunogenicity): Incidence of AEs/SAEs/AESIs assessed through clinical signs and symptoms, vital signs, physical examination, laboratory tests (complete blood count, urinalysis, and blood biochemistry), coagulation function [prothrombin time (PT), thrombin time (TT), international normalized ratio (INR), fibrinogen (FIB), activated partial thromboplastin time (APTT), D-dimer], FDP, 12-lead electrocardiogram, injection site reactions, hypersensitivity/allergic reactions, thrombotic events, etc.; incidence of drug-related AEs/SAEs/AESIs; number and incidence of subjects with anti-drug antibodies (ADA) and neutralizing antibodies.

Secondary endpoints: Single-dose PK parameters: $t_{1/2z}$, C_{max} , T_{max} , AUC_{0-t} , $AUC_{0-\infty}$, CL_z/F , V_z/F , MRT , etc.;

Exploratory endpoints (PD parameters): Protac-APTT (Protac-induced protein C-activated APTT assay), protein C, prothrombin time (PT), thrombin generation assay (TGA).

Part B / Part C:

Primary endpoint: Treatment-based annualized bleeding rate (ABR).

Secondary endpoints (PK parameters): Multiple-dose PK parameters: $T_{max,ss}$, $C_{max,ss}$, AUC_{0-t} , CL_{ss}/F , $C_{min,ss}$, $C_{av,ss}$, $AUC_{0-\tau,ss}$, and degree of fluctuation at steady state (DF), etc.; if data permit, parameters such as $t_{1/2z}$, $AUC_{0-\infty}$, V_z/F , MRT, and λ_z will be calculated;

Secondary endpoints (other efficacy): Treatment-based annualized spontaneous bleeding rate, treatment-based annualized total joint bleeding rate; treatment-based annualized menorrhagia bleeding rate (applicable only to female patients of childbearing age with menstruation who have congenital coagulation Factor VII deficiency). Change from baseline in the Hemophilia Joint Health Score (HJHS) (Hemophilia A and B patients); change from baseline in the EuroQol-5 Dimension-5 Level (EQ-5D-5L) questionnaire.

Secondary endpoints (safety and immunogenicity parameters): Same as Part A.

Exploratory endpoints (PD parameters): Protac-APTT (Protac-induced protein C-activated APTT assay), protein C, prothrombin time (PT), thrombin generation assay (TGA), pro-inflammatory cytokines (IL-1 β , IL-6, TNF- α).

Trial Design

This trial consists of three parts: Part A, Part B, and Part C. Part A is an open-label, single-dose, dose-escalation Phase I trial. Part B is a two-dose, open-label, multiple-dose efficacy-exploratory Phase IIa trial for prophylactic treatment. Part C is a randomized, open-label, multiple-dose efficacy-exploratory Phase IIb trial for prophylactic treatment.

Part A:

This part employs a combined approach of accelerated titration and a "3+3" design for dose escalation.

Six dose cohorts are designed: 0.025 mg/kg, 0.05 mg/kg, 0.1 mg/kg, 0.2 mg/kg, 0.4 mg/kg, and 0.8 mg/kg. Starting from Cohort 1 (0.025 mg/kg, starting dose), the safety, tolerability, pharmacokinetic, and pharmacodynamic characteristics of each dose cohort will be evaluated sequentially.

[figure not shown]

Figure 3-1: Schematic Diagram of Dose Escalation Plan (Part A)

Subjects enrolled in Cohort 3 and subsequent dose cohorts, after completion of the Day 29 safety data review and assessment following dosing, will continue follow-up to Day 85 post-dose for immunogenicity and relevant safety assessments and PK/PD sample collection before exiting the trial. Subjects in Cohort 1, after completing the 29-day follow-up, will continue follow-up per the amended protocol (Ver 1.1) to Day 57 post-dose. Subjects in Cohort 2, after completing the 57-day follow-up per the protocol (Ver 1.1), will continue follow-up per the amended protocol (Ver 1.2) to Day 85 post-dose.

Part B:

This part is a two-dose, open-label, multiple-dose efficacy-exploratory Phase IIa trial for prophylactic treatment. Two dose groups will be selected: 0.05 mg/kg (with a loading dose of 0.1 mg/kg for the first injection) and 0.1 mg/kg (with a loading dose of 0.2 mg/kg for the first injection), with 12 subjects enrolled per dose group.

Eligible patients will enter a 3-month (12-week) treatment period, with dosing every 2 weeks for a total of 6 doses, along with PK/PD blood sample collection. After 12 weeks, subjects may enter a 3-month (12-week) extension treatment period, with dosing every 2 weeks for a total of 6 doses, along with PK/PD blood sample collection, and will exit the trial after completion of a 56-day safety assessment following the last dose.

[figure not shown]

Figure 3-2: Schematic Diagram of Trial Design (Part B)

Part C:

This part is a randomized, open-label, multiple-dose efficacy-exploratory Phase IIb trial for prophylactic treatment. Three groups (A, B, C) will be selected, each enrolling 12 subjects, with the following dosing regimens:

Group A: Dose 0.4 mg/kg, Dosing frequency once every 4 weeks (Q4W)

Group B: Dose 0.4 mg/kg, Dosing frequency once every 6 weeks (Q6W)

Group C: Dose 0.4 mg/kg, Dosing frequency once every 8 weeks (Q8W)

Eligible patients will be randomized in a 1:1:1 ratio to Group A (0.4 mg/kg Q4W), Group B (0.4 mg/kg Q6W), or Group C (0.4 mg/kg Q8W), and will then enter a 6-month (24-week) treatment period. During the treatment period, Groups A, B, and C will receive 6, 4, and 3 doses, respectively. After the treatment period, subjects may enter an extension treatment period of up to 6 months (24 weeks). During the extension treatment period, Groups A, B, and C will receive up to 6, 4, and 3 additional doses, respectively. Efficacy endpoints will be collected at 28 days (Group A), 42 days (Group B), or 56 days (Group C) after the last dose, completing the final visit of the extension treatment period. The follow-up period extends to 84 days after the last dose. See Figure 3-3 for trial design details.

[figure not shown]

Figure 3-3: Schematic Diagram of Trial Design (Part C)

Sample Size

Part A: For the Hemophilia A/B indication, 6 dose cohorts are prespecified, with approximately 16–33 evaluable subjects planned. Cohort 1 will enroll 1–3 subjects, and each subsequent cohort will enroll 3–6 subjects.

Part B: Two dose groups are planned, with 12 subjects per group, for a total enrollment of 24 subjects, including patients with Hemophilia A/B and congenital coagulation Factor VII deficiency.

Part C: Three groups are planned, with 12 subjects per group, for a total enrollment of 36 subjects, including patients with Hemophilia A/B and congenital coagulation Factor VII deficiency.

Trial Duration

Part A: From screening of the first subject to the last visit of the last subject, the estimated trial duration is 11 months.

Part B: From screening of the first subject to the last visit of the last subject, the estimated trial duration is 15 months.

Part C: From screening of the first subject to the last visit of the last subject, the estimated trial duration is 21 months.

Subject Duration

Part A: For each subject from signing informed consent through completion of all protocol-specified visits, the expected maximum duration is approximately 115 days.

Part B: For each subject from signing informed consent through completion of all protocol-specified visits, the expected maximum duration is approximately 241 days. Among these, female patients with congenital coagulation Factor VII deficiency have an expected maximum duration of approximately 255 days.

Part C: For subjects in Group A, from signing informed consent through completion of all protocol-specified visits, the expected maximum duration is approximately 424 days. Among these, female patients with congenital coagulation Factor VII deficiency have an expected maximum duration of approximately 438 days. For subjects in Group B, the expected maximum duration is approximately 410 days. Among these, female patients with congenital coagulation Factor VII deficiency have an expected maximum duration of approximately 424 days. For subjects in Group C, the expected maximum duration is approximately 396 days. Among these, female patients with congenital coagulation Factor VII deficiency have an expected maximum duration of approximately 410 days.

Subject Selection

Inclusion Criteria:

1. Age ≥ 18 years and ≤ 65 years at the time of signing informed consent, regardless of sex;
2. Clinically diagnosed with Hemophilia A or B or congenital coagulation Factor VII deficiency, and must meet the following criteria:
 - a. Hemophilia A or B patients with historical or screening FVIII activity level $< 1\%$ or FIX activity level $\leq 2\%$;

Note: Hemophilia A or B patients with or without inhibitors may be enrolled. For patients without inhibitors (inhibitor titer < 0.6 BU/mL), they must have previously received coagulation factor treatment with exposure days (EDs) > 50 days.

- b. Congenital coagulation Factor VII deficiency patients with historical or screening FVII activity $< 10\%$;
3. Part A only: Received on-demand treatment with FVIII, FIX, recombinant human coagulation Factor VIIa (rFVIIa), or PCC for bleeding events within 1 month prior to screening;
4. Part B/Part C only: Accessible bleeding and treatment records (factor replacement or bypassing agent therapy) for at least 3 months prior to enrollment. Hemophilia A or

B patients must have received on-demand treatment with ≥ 3 treated de novo bleeding episodes within 3 months prior to enrollment. Congenital coagulation Factor VII deficiency patients must have ≥ 2 treated de novo bleeding episodes within 3 months prior to enrollment;

5. No active bleeding symptoms prior to first dosing;
6. The subject or a legally acceptable representative has a full understanding of and can comply with the protocol requirements, has the willingness to complete the study as planned, and voluntarily agrees to provide biological samples for testing as required by the protocol;
7. The subject is able to understand the procedures and methods of this clinical trial, has been fully informed, and voluntarily participates in the trial by personally signing the informed consent form.

Exclusion Criteria:

1. Subjects with a known history of hypersensitivity to the investigational medicinal product or any of its components;
2. Intolerance to subcutaneous injection or presence of other local skin abnormalities or dermatological conditions that may affect administration and safety assessment;
3. Subjects meeting any of the following criteria at screening:
 - a. Hemoglobin < 60 g/L;
 - b. Platelet count $< 100 \times 10^9/L$;
 - c. Hepatic or renal impairment: alanine aminotransferase (ALT) or aspartate aminotransferase (AST) $\geq 2.5 \times$ upper limit of normal (ULN), or total bilirubin $\geq 1.5 \times$ ULN; or serum creatinine (Cr) $\geq 1.5 \times$ ULN;
4. Positive result(s) for hepatitis B virus surface antigen (HBsAg), anti-human immunodeficiency virus (HIV) antibody, and/or Treponema pallidum-specific antibody;
5. Clinically diagnosed with active hepatitis C;
6. Any other bleeding disorder or any other disease causing significant coagulation abnormalities (e.g., platelet disorders, vitamin K deficiency, etc.) other than Hemophilia A or B and congenital coagulation Factor VII deficiency;
7. Protein C deficiency or protein S deficiency;
8. History of or current thrombosis, family history of thrombosis, or history of thrombophilia prior to signing informed consent;
9. Intracranial hemorrhage due to Hemophilia A or B or congenital coagulation Factor VII deficiency within 2 years prior to screening;
10. Severe cardiac disease, such as unstable angina, congestive heart failure (New York Heart Association Class \geq III), severe arrhythmia (QTc interval > 450 ms,

corrected by Fridericia's formula), or uncontrolled hypertension (systolic blood pressure ≥ 160 mmHg or diastolic blood pressure ≥ 95 mmHg);

11. Received recombinant human coagulation Factor VIIa (rFVIIa) within 48 hours prior to first dosing; received any FVIII-containing product within 72 hours prior to first dosing; received any FIX-containing product within 96 hours prior to first dosing; long-acting products of the above have not completed a washout of 5 half-lives;
12. Used or requires use of any anticoagulant, antifibrinolytic agent, or chemical drug, biological product, or traditional Chinese medicine affecting platelet function, including nonsteroidal anti-inflammatory drugs (NSAIDs) such as aspirin, within 1 week prior to first dosing or during the trial;
13. Received whole blood or plasma therapy within 2 weeks prior to first dosing;
14. Received emicizumab treatment within 6 months prior to first dosing;
15. Received or planned to receive vaccination within 4 weeks prior to first dosing or during the trial;
16. Underwent major surgery (e.g., orthopedic surgery, abdominal surgery) within 1 month prior to first dosing, or planned to undergo surgery during the study;
17. Enrolled in another clinical trial within 1 month prior to first dosing;
18. History of drug abuse or alcoholism (alcoholism criteria: long-term drinking history exceeding 5 years, equivalent to ethanol intake ≥ 40 g/day, or heavy drinking within 2 weeks, equivalent to ethanol intake > 80 g/day. Ethanol amount (g) conversion formula = alcohol volume (mL) \times ethanol content (%) $\times 0.8$);
19. Psychiatric illness or significant mental impairment, or incapacity or lack of cognitive ability due to other reasons;
20. Plans to have children or donate sperm during the entire trial period up to 6 months after the last dose, or unwilling to use effective physical contraceptive measures (e.g., condoms);
21. Subjects with clinically significant disease or other conditions that the investigator considers unsuitable for participation in the clinical trial (e.g., the patient cannot benefit from the clinical trial);
22. Subjects deemed by the investigator to have poor compliance, rendering efficacy evaluation impossible or with low likelihood of completing the planned treatment course and follow-up.

Dose Selection and Rationale

In vitro inhibition studies showed: In human coagulation factor-deficient plasma at concentrations of 0.303–0.445 $\mu\text{g/mL}$, and in normal cynomolgus monkey plasma and human plasma at concentrations of 0.455 and 0.439 $\mu\text{g/mL}$, respectively, the inhibition rate of Protac-APTT reached approximately 90%.

In tail-clip bleeding studies in PROC+/+F8-/- and PROC+/+F9-/- mice, subcutaneous administration of SR604 at doses of 0.05, 0.1, and 0.2 mg/kg significantly reduced tail-clip bleeding in humanized protein C hemophilia A and B model mice. At the 0.2 mg/kg dose, SR604 completely achieved a prophylactic bleeding prevention effect.

In a standalone pharmacokinetic study in PROC+/+F8-/- mice, SR604 concentrations at 24 h after subcutaneous injection of 0.05 and 0.2 mg/kg were 0.506 µg/mL and 1.36 µg/mL, respectively. A concentration of 0.506 µg/mL associated with the 0.05 mg/kg dose in mice was considered the minimum relevant trough level of SR604 to provide a clinically relevant pharmacodynamic response in humans.

To determine the efficacy of SR604 on intra-articular bleeding, a knee joint injury experiment simulating intra-articular bleeding was conducted in PROC+/+;F8-/- or PROC+/+;F9-/- mice. The results showed that in PROC+/+;F8-/- or PROC+/+;F9-/- mice, the reduction in knee joint swelling after SR604 pretreatment was comparable to that after FVIII or PCC pretreatment. SR604 pretreatment significantly reduced inflammation and hyperplasia in the synovium and matrix lining of PROC+/+;F8-/- or PROC+/+;F9-/- mice. To evaluate the cytoprotective and endothelial barrier functions of APC in humanized protein C hemophilia mice treated with SR604, assessment was performed in a lipopolysaccharide (LPS)-induced systemic inflammation model. The results showed that SR604 not only did not exacerbate the sublethal LPS response in PROC+/+;F8-/- or PROC+/+;F9-/- mice, but H&E staining images and pan-inflammatory cell marker (CD45) immunostaining also showed that SR604 could reduce LPS-induced inflammatory cell infiltration in lung tissue sections of PROC+/+;F8-/- or PROC+/+;F9-/- mice.

Additionally, studies have shown that histones are associated with various pathologies, including inflammation, cell death, and organ failure, while activated protein C (APC) can cleave histones, thereby reducing histone-induced inflammatory or cytotoxic responses. Some of our in vitro studies showed that SR604 only affected and inhibited the anticoagulant function of APC, while maintaining the cytoprotective and endothelial barrier functions of APC, and it was also found that in the presence of SR604, the histone-cleaving activity of APC was enhanced.

A single-dose toxicity study in cynomolgus monkeys showed: After intravenous administration at 0.3 mg/kg and subcutaneous administration at 0.06, 0.3, and 1.5 mg/kg, the C_{max} following subcutaneous administration at the same dose was approximately 0.5 times that of intravenous administration, and the exposure was approximately 0.84 times that of intravenous administration. Based on a modified Protac-APTT coagulation assay, the estimated in vivo effective concentrations of SR604 for 90%, 80%, and 50% target inhibition were 1.21, 0.641, and 0.225 µg/mL, respectively.

Based on the above nonclinical pharmacodynamic study results and nonclinical pharmacokinetic PK data, the minimum pharmacodynamic concentration of SR604 was

set at 0.506 µg/mL (close to the in vitro 90% inhibition concentration). Through modeling and simulation, it was predicted that a single subcutaneous injection of 0.05 mg/kg in hemophilia patients would achieve a peak concentration reaching the predicted minimum effective concentration; a single subcutaneous injection of 0.1 mg/kg would maintain concentrations at or above the minimum effective concentration for approximately 16 days; and a single subcutaneous injection of 0.2 mg/kg would maintain concentrations at or above the minimum effective concentration for approximately 29 days.

In a single-dose toxicity study in mice, the maximum tolerated dose was 100 mg/kg (NOAEL). Referring to relevant guidelines and guidance documents, calculated for an adult body weight of 60 kg, the human equivalent dose (HED) is 8.13 mg/kg (100/12.3). Considering safety factors of 10 or 5, the corresponding maximum recommended starting dose (MRSD) is 0.813 mg/kg or 1.626 mg/kg, respectively.

In a single-dose intravenous and subcutaneous pharmacokinetic study in cynomolgus monkeys, doses of 0.3 mg/kg IV and 0.06, 0.3, and 1.5 mg/kg SC were administered. At the 1.5 mg/kg dose, one animal was euthanized due to moribund condition, and multi-organ thrombosis was considered the likely cause. The moribund condition of this animal was considered possibly related to the test article. In a repeat-dose toxicity study in healthy cynomolgus monkeys, subcutaneous injections were administered at 0.1, 0.3, and 1.5 mg/kg every 2 weeks for 4 weeks, for a total of 3 doses. In the 1.5 mg/kg dose group, two animals developed tail ulceration prior to dosing, and the pharmacological effect of the test article exacerbated distal tissue abnormalities post-dosing, ultimately resulting in moribund condition/euthanasia. In the 0.1 and 0.3 mg/kg groups, apart from tissue injury caused by pharmacological exacerbation of ulceration/scabbing, no other significant abnormalities were observed. Therefore, the NOAEL was established at 0.3 mg/kg. Referring to relevant guidelines and guidance documents, calculated for an adult body weight of 60 kg, the HED is 0.097 mg/kg (0.3/3.1). Given that the preclinical toxicity studies were conducted in healthy cynomolgus monkeys, while the clinical trial will be conducted in a patient population, a safety factor of 5 was considered, resulting in an MRSD of 0.019 mg/kg.

In a 14-week repeat subcutaneous and intravenous toxicity study in cynomolgus monkeys (with an 8-week recovery period), SR604 was administered subcutaneously at 0.03, 0.1, and 0.3 mg/kg every 2 weeks for 14 weeks, for a total of 8 doses, followed by an 8-week recovery period. No mortality or moribund condition was observed in animals of any dose group. Clinical observations included tail ulceration/scabbing, with distal tail necrosis due to pharmacological exacerbation of injury. Transient slight elevation of IL-6 was observed in individual animals. At the end of the 8-week recovery period, the above changes were reversible. No other systemic toxicological changes were observed. No significant abnormalities were observed in safety pharmacology parameters of the central nervous system, cardiovascular system, respiratory system, or other organs and tissues (including male and female reproductive organs) in any dose group. SR604 was

administered intravenously at 0.3 mg/kg every 2 weeks for 14 weeks, for a total of 8 doses, followed by an 8-week recovery period. At this dose, clinical observations included tail ulceration/scabbing, and post-dosing observations showed pharmacologically exacerbated swelling and necrosis of the proximal/middle/distal tail, secondary clinical pathology abnormalities (prolonged APTT, elevated FIB, decreased RBC, HGB, HCT, slight increase in Retic), and transient elevation of IL-6. No abnormalities were observed in the central nervous system or other organs and tissues (including male and female reproductive organs). At the end of the 8-week recovery period, the above changes were reversible. SR604 was administered subcutaneously at concentrations of 0.2, 0.67, and 2 mg/mL (doses of 0.03, 0.1, and 0.3 mg/kg) and intravenously at 2 mg/mL (dose of 0.3 mg/kg) every 2 weeks for 14 weeks, for a total of 8 doses. No local irritation reactions were observed at the injection sites in any subcutaneous or intravenous administration group.

Based on the comprehensive results of nonclinical pharmacodynamic, pharmacokinetic, and toxicity studies, the starting dose for the clinical trial is proposed to be 0.025 mg/kg. This dose is 12-fold lower than the NOAEL in monkeys (0.3 mg/kg) and 4,000-fold lower than the well-tolerated 100 mg/kg single SC dose in PROC+/+F8/- and PROC+/+F9/- mice (see Table 3-1). Subsequent dose escalation will proceed at 0.05 mg/kg, 0.1 mg/kg, 0.2 mg/kg, 0.4 mg/kg, and 0.8 mg/kg.

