Screening Period: Subjects enter the screening period after signing the informed consent form. Screening assessments and evaluations will be completed per the visit schedule. The screening period shall not exceed 2 weeks (if subjects use rFVIIa, FVIII, FIX, or PCC for on-demand treatment of bleeding events prior to planned dosing, or due to epidemic control measures, or other force majeure factors, the screening period may be extended, but not to exceed 4 weeks; for patients with congenital coagulation Factor

VII deficiency, it may be extended to D-42 at most). Subjects who meet all inclusion criteria and none of the exclusion criteria will enter the trial.

Treatment Period: Eligible patients will enter a 3-month (12-week) treatment period, with dosing every 2 weeks for a total of 6 doses. Specific dosing details are provided in the dosage and administration section. Patients will complete efficacy and safety assessments per the visit schedule, along with PK/PD blood sample collection.

Extension Treatment Period: After completing the treatment period, subjects will enter a 3-month (12-week) extension treatment period, with dosing every 2 weeks for a total of 6 doses. Specific dosing details are provided in the dosage and administration section. Patients will complete efficacy and safety assessments per the visit schedule, along with PK/PD blood sample collection.

When patients experience breakthrough bleeding requiring treatment, the occurrence and treatment of bleeding events will be collected. The investigator will select appropriate therapeutic agents and measures based on the patient's condition. Commercially available human coagulation Factor VIII/IX (plasma-derived or recombinant), recombinant human coagulation Factor VIIa (rFVIIa), or PCC may be used for bleeding treatment. Recommended treatment regimens are provided in Table 6-1. The specific dose and treatment course may be determined by the investigator based on the bleeding site, severity, and hemostatic response.

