Part C: Consists of a screening period, treatment period, extension treatment period, and follow-up period.

Screening Period: Same as Part B.

Treatment Period: Eligible patients will enter a 6-month (24-week) treatment period. Group A will be dosed once every 4 weeks for a total of 6 doses; Group B will be dosed once every 6 weeks for a total of 4 doses; Group C will be dosed once every 8 weeks for a total of 3 doses. Specific dosing details are provided in the dosage and administration section. Patients will complete efficacy and safety assessments per the visit schedule, along with PK/PD blood sample collection.

Extension Treatment Period: After completing the treatment period, subjects will enter an extension treatment period of up to 6 months (24 weeks). Group A will be dosed once every 4 weeks for up to 6 additional doses; Group B will be dosed once every 6 weeks for up to 4 additional doses; Group C will be dosed once every 8 weeks for up to 3 additional doses. Patients will complete efficacy and safety assessments per the visit schedule, along with PK/PD blood sample collection.

Follow-up Period: At 84 days after the last dose/early withdrawal, safety assessments including vital signs, physical examination, laboratory tests (including complete blood count, urinalysis, and blood biochemistry), coagulation function, FDP, 12-lead ECG, anti-SR604 antibodies (ADA), and neutralizing antibodies will be performed. Bleeding events and their treatment, adverse events, and concomitant medications/treatments will be recorded. If safety evaluation parameters are abnormal, follow-up must continue until values return to normal, are deemed not clinically significant, are stable, or return to baseline.

Pharmacokinetics/Pharmacodynamics (PK/PD)

Biological Sample Collection:

All subjects participating in this trial will have biological samples collected at designated timepoints for PK/PD analysis, following the initially proposed sampling schedule. During the trial, based on the PK/PD data and analysis results obtained from completed dose cohorts, the PK/PD biological sample collection timepoints for subjects in subsequent dose cohorts may be appropriately adjusted as necessary.

Biological sample collection will be performed by authorized or trained medical personnel according to the requirements of the testing laboratory.

Table 8-2 PK/PD Sampling Timepoints and Time Windows (Part A)

Collection Timepoint	PK Sample	PD Sample	Tolerance Window

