1. At 12 weeks and 24 weeks of treatment, treatment-based annualized spontaneous bleeding rate;
2. At 12 weeks and 24 weeks of treatment, treatment-based annualized total joint bleeding rate (AJBR);
3. At 12 weeks and 24 weeks of treatment, treatment-based annualized menorrhagia bleeding rate (applicable only to female patients of childbearing age with menstruation who have congenital coagulation Factor VII deficiency);
4. At 12 weeks and 24 weeks of treatment, change from baseline in the Hemophilia Joint Health Score (HJHS) (Hemophilia A and B patients);
5. At 12 weeks and 24 weeks of treatment, change from baseline in the EuroQol-5 Dimension-5 Level (EQ-5D-5L) questionnaire.

Efficacy Parameters (Part C)

Primary efficacy parameters:

At 24 weeks of treatment and during the treatment period (including treatment and extension treatment periods), treatment-based annualized bleeding rate (ABR).

The following formulas can be used for calculation:

ABR at 24 weeks = (Number of treated bleeding episodes within the dosing interval after the last dose during the 24-week treatment period x 365.25) / (Date of last dose during the 24-week treatment period - Date of first dose + dosing interval)

ABR during the treatment period (including treatment period and extension treatment period) = (Number of treated bleeding episodes within the dosing interval after the last dose x 365.25) / (Date of last dose - Date of first dose + dosing interval)

Note: Total bleeding includes spontaneous and traumatic bleeding. A treated bleeding episode refers to a bleeding event for which factor replacement or bypassing agent therapy was administered.

The 'dosing interval' for the Q4W group is 28 days; for Q6W it is 42 days; for Q8W it is 56 days.

Secondary efficacy parameters:

1. At 24 weeks of treatment and during the treatment period (including treatment and extension treatment periods), treatment-based annualized spontaneous bleeding rate;
2. At 24 weeks of treatment and during the treatment period (including treatment and extension treatment periods), treatment-based annualized total joint bleeding rate (AJBR);
3. At 24 weeks of treatment and during the treatment period (including treatment and extension treatment periods), treatment-based annualized menorrhagia bleeding rate (applicable only to female patients of childbearing age with menstruation who have congenital coagulation Factor VII deficiency);

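### Part C eligibility names neither breastfeeding nor current pregnancy, so a breastfeeding woman who plans no further child is kept out only by investigator judgement

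*Protocol*

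**What the plan says.** The eligibility list under Subject Selection is not split by part, apart from inclusion items 3 and 4, so it governs Part C. Women are eligible: inclusion item 1 reads "Age ≥ 18 years and ≤ 65 years at the time of signing informed consent, regardless of sex". They are also expected. A Part C secondary efficacy parameter, the annualized menorrhagia bleeding rate, is "applicable only to female patients of childbearing age with menstruation who have congenital coagulation Factor VII deficiency", and Subject Duration gives separate, longer maxima for women with Factor VII deficiency.

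Reproductive status is addressed only in exclusion item 20. Its first limb is "Plans to have children or donate sperm during the entire trial period up to 6 months after the last dose"; its second is being "unwilling to use effective physical contraceptive measures (e.g., condoms"). Item 21 lets the investigator exclude for "other conditions that the investigator considers unsuitable for participation in the clinical trial", and item 22 concerns expected poor compliance.

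The entry rule, in the Part B screening paragraph of Trial Procedures, is "Subjects who meet all inclusion criteria and none of the exclusion criteria will enter the trial". Part C adopts it with "Screening Period: Same as Part B".

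**The concern.** Item 20 looks forward: it asks what a subject plans and what contraception she will accept. It does not ask about her present state. Breastfeeding is a present state that involves no future plan, so the item does not reach it.

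The consequence falls on an infant who is not a trial subject. Dose Selection and Rationale describes SR604 as blocking the anticoagulant function of activated protein C. It reports one monkey euthanized at 1.5 mg/kg, with multi-organ thrombosis the likely cause and a possible relation to the drug. The 14-week monkey study found no abnormality of the reproductive organs, but that is not lactation data, and the text shown contains none. With transfer into milk unknown, one would expect a mandatory exclusion rather than a decision taken separately at each of the 6 planned sites. The same list makes mandatory rules for other foreseeable matters such as vaccination, alcohol intake and sperm donation.

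**Working it through.** The main check is a reading of the text. The arithmetic only describes how long a mother would be exposed.

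**1. Count the items.** Inclusion items run 1–7 and exclusion items 1–22, with no gap in numbering. Items naming breastfeeding: 0 of 7 and 0 of 22. Items naming current pregnancy: 0 of 7 and 0 of 22.

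**2. Trace one case.** Take a breastfeeding woman with Factor VII deficiency who is otherwise eligible.

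| Criterion | Does it exclude her for breastfeeding? |
|---|---|
| Inclusion 1–7 | No; sex is unrestricted and lactation is not mentioned |
| Exclusion 1–19 | No; none concerns reproductive status |
| Exclusion 20, first limb | No, if she plans no further child |
| Exclusion 20, second limb | No, if she accepts condoms |
| Exclusion 21–22 | Only if the investigator so judges |

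Under the entry rule she then enters the trial.

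**3. Pregnancy separately.** A woman known to be pregnant and intending to deliver can be read as planning to have a child within the trial window, so the first limb arguably covers her. An unrecognised pregnancy is caught only by a timely test. The visit schedule is not shown, so whether one is planned cannot be judged. A pregnancy test would not detect breastfeeding in any case.

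**4. Doses for one affected woman** (counts from Trial Design, Part C; 0.4 mg/kg each).

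| Group | 24-week period | With full extension |
|---|---|---|
| A (Q4W) | 6 × 0.4 = 2.4 mg/kg | 12 × 0.4 = 4.8 mg/kg |
| B (Q6W) | 4 × 0.4 = 1.6 mg/kg | 8 × 0.4 = 3.2 mg/kg |
| C (Q8W) | 3 × 0.4 = 1.2 mg/kg | 6 × 0.4 = 2.4 mg/kg |

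**5. Clearance after the last dose**, taken as 5 × half-life, with half-lives from the preliminary PK in Dose Selection and Rationale:

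- 0.1 mg/kg (mean of 3 patients): 5 × 12.77 = 63.9 days
- 0.05 mg/kg (mean of 3 patients): 5 × 13.49 = 67.5 days
- 0.025 mg/kg (1 patient): 5 × 7.8 = 39.0 days

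The half-life at 0.4 mg/kg is not given; it is assumed to lie in this range.

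**6. Exposure window without extension.** The last treatment-period dose falls on D141 (A), D127 (B) or D113 (C). Adding 64 days gives exposure from D1 to about D205, D191 or D177.

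**The case against.** The other side accepts the textual fact and disputes its weight.

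- **Pregnancy is largely covered already.** Maximum durations of about 396–438 days exceed any pregnancy, so a woman carrying to term would have a child within the window of item 20. This stands for a known, continuing pregnancy. It does not help with breastfeeding.
- **The case is rare and not unguarded.** She must meet the factor-activity and recent-bleed criteria, plan no further child, accept condoms, and face an investigator who raises no objection. Item 21 is not limited to disease. The rarity stands. The guard is real but discretionary, and its only example is a patient who cannot benefit. A breastfeeding woman may well benefit; the open question is her infant.
- **No infant harm is shown.** Maternal doses and clearance are not infant exposure, and a dose rationale is not a full toxicology summary. This stands: the figures give the duration of maternal exposure and nothing more. The case for exclusion rests on transfer being unknown in the text shown.
- **The tests may already be scheduled.** The visit schedule is not shown. This stands, and it is why the tests are to be added only if absent.
- **The change may come too late.** The version is dated 13 January 2026 and Part C's enrolment status is not stated. If enrolment were complete, a new eligibility rule would protect no one in this part.

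**Conclusion.** The concern holds. As written, the Part C criteria contain no mandatory bar to dosing a breastfeeding woman who plans no further child and accepts physical contraception. Current pregnancy is also unnamed, but that is the weaker half, since a known pregnancy is arguably within item 20.

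The number affected is unknown and probably small: Part C plans 36 subjects, and the Protocol sets no number or minimum of women. For one such woman, exposure would run through the treatment period and about 64 days beyond the last dose (39 to 67 days over the reported half-lives). No endpoint, estimate or analysis is affected. It should be fixed as an inexpensive safety improvement; it is not a flaw in the trial's evidence. Confidence is moderate, because the visit schedule and the full toxicology data are not in the text at hand. The value of the change also depends on Part C still having subjects to enrol.

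**What to change.** For Part C, extend exclusion item 20 with wording such as: *or women who are currently pregnant or breastfeeding; women of childbearing potential must have a negative pregnancy test at screening and before the first dose on D1.* Check that the visit schedule holds both tests, and add them only if it does not.

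This fits the sponsor's own intent, since the item already bars planned children until 6 months after the last dose. Part B needs no change, because enrolment and first dosing of its 24 subjects are complete.

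The cost is a short eligibility amendment to be approved and rolled out at the 6 planned sites, and at most two inexpensive tests per woman of childbearing potential. The downside is that an occasional woman is excluded or deferred.
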